#### **6.4 Cohort 2**

- 6.4.1 Raw data from all the study sensors will be collected as described in Section 6.2 (Non-invasive readings).
- 6.4.2 The anesthesiologist and/or anesthesia providers will be able to monitor and use FDA-cleared PSI Rev 1.X to supplement SOC procedures in managing anesthesia.
- 6.4.3 All study data as described in this Clinical Investigation Plan will be provided to Masimo and analyzed.

#### **6.5 Cohort 3**

- 6.5.1 Raw data from all the study sensors will be collected as described in Section 6.2 (Non-invasive readings).
- 6.5.2 The anesthesiologist and/or anesthesia providers will be able to monitor and use the investigational PSI Rev 2.X to supplement SOC procedures in managing anesthesia.
- 6.5.3 At the anesthesiologist's and/or anesthesia providers' discretion, he/she can discontinue his/her reliance on PSI and can revert to standard of care anesthesia procedures at any time to safeguard subject health, safety, and welfare.
- 6.5.4 All study data as described in this Clinical Investigation Plan will be provided to Masimo and analyzed.

### **7 SAMPLE SIZE AND STATISTICAL CONSIDERATIONS**

In a two sample t-test, such as in this case when two different Cohorts (experimental vs. control) are being compared, the desired statistical power is usually set at 0.80. This convention implies a four-to-one tradeoff between  $\beta$  and  $\alpha$  ( $\beta$  is the probability of a Type II error (false negatives), and  $\alpha$  is the probability of a Type I error (false positives); 0.2 and 0.05 are conventional values for  $\beta$  and  $\alpha$ , respectively). The Cohen's d value, which is the expected difference between the means of the experimental group and the control group divided by the expected standard deviation, is usually set at 0.80. Assuming that experimental and control groups have equal sample sizes, and assuming that both groups have normal distributions, this combination of statistical power and Cohen's d yields an estimated sample size of 26 samples per Cohort/group.

The current clinical Investigation plan defines enrollment of up to 50 subjects per Cohort, which would provide more than enough samples per Cohort to detect a difference between the outcome variables of the different Cohorts.

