**4 SUBJECT SELECTION AND WITHDRAWAL**

**4.1 Number of Subjects**

Up to 150 subjects undergoing general surgery may be enrolled into this study. Up to 50 subjects may be enrolled per Cohort.

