**4.2 Inclusion Criteria**

- 18 years of age or older
- ASA status of I, II, and III
- Subjects undergoing general surgery
- Neurologically intact patients (e.g. no history or presence of traumatic brain injuries, neurological diseases, etc.)

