**4.5 Subject Recruitment and Screening**

Following identification of a potential subject, the patient will be approached by the principal investigator or a designated research staff member, who will explain the purpose and procedures of the study. If the patient express interest in participating in the study, they will be asked to read the written Informed Consent Form in English or Spanish depending on the patient's language preference.

All items of the Informed Consent will be explained in a way that is easily understandable, for either English or Spanish speaking subjects. The patient will be given adequate time to read through the Informed Consent, and they will be given adequate time and privacy to consider the decision of whether or not to sign the Informed Consent Form. Once all of the

patient's questions have been answered and the Informed Consent Form signed, the patient is now adequately consented. Now the patient will be enrolled as a study subject, at which time the subject will be assigned a study identification number or enrollment number.

All subjects will have their medical history reviewed at the time of screening by either the PI or the study staff who is delegated for this task. Subjects will be evaluated based on the inclusion and exclusion criteria to determine eligibility to be enrolled into the study. If a subject is deemed ineligible after screening, the subject will be withdrawn from the study.

Information regarding the subject's demographic (including, but not limited to age, weight, race, ethnicity, comorbidities, medications, etc.), preexisting allergies, skin abnormalities, and other preexisting diseases/conditions that may be relevant to the study will be recorded within a paper-based Case Report Form (CRF).

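### The cohorts are consecutive and unrandomised, yet no covariate-adjusted comparison is specified: Section 9.7 should fix one, mainly to reduce bias from measured case mix.

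*Combined protocol and SAP*

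**What the plan says.** - **Allocation.** Section 6.1 fills Cohort 1 first, then Cohort 2, then Cohort 3, with equal sizes. Section 4.1 sets the ceiling: "Up to 50 subjects may be enrolled per Cohort". There is no randomisation.
- **Test.** Section 7 names one between-cohort test, while justifying the sample size: "In a two sample t-test, such as in this case when two different Cohorts (experimental vs. control) are being compared". With conventional error rates and Cohen's d of 0.80, this "yields an estimated sample size of 26 samples per Cohort/group". No covariate is mentioned.
- **Analysis section.** Section 9.7 lists descriptive statistics, regression testing and accuracy measures as things the analysis may include. It says that Cohorts 2 and 3 may be compared with each other and each with Cohort 1. It gives no model, outcome or covariate list, and sponsor personnel do the analysis after the study is complete.
- **Population.** Section 4.2 admits adults with no upper age limit having general surgery, with "ASA status of I, II, and III".
- **Data held before anesthesia.** Section 4.5 records on the CRF items that include "age, weight, race, ethnicity, comorbidities, medications, etc". ASA class is not in that list. Section 9.5.2 says the CRF covers the inclusion and exclusion criteria.
- **Use of the comparison.** Aim Four (Section 2.1) judges the investigational PSI against the current PSI on somatic events, total anesthetic drug, wake-up time and PSI versus OAA/S.

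**The concern.** Nothing in the design balances patients between consecutive blocks of up to 50, and eligibility is wide enough for the blocks to differ. Section 1.1 says there is no reference standard for PSI and that algorithms have been compared through clinical outcomes. A difference in age, comorbidity or medication between the Cohort 2 and Cohort 3 blocks could therefore be read as a difference between algorithms.

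These characteristics are fixed before anesthesia, so PSI guidance cannot affect them and they are safe to adjust for. An unadjusted t-test leaves any imbalance in the estimate and their outcome variation in the error term. An optional, unspecified regression does not cure this, because the covariates could be chosen after the results are known.

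**Working it through.** **1. The plan's own figure.** Inputs from Section 7: power 0.80, alpha 0.05, d = 0.80, equal groups. Sidedness is not stated. The two-sided two-sample t-test (noncentral t) gives n = 25.52, rounded up to 26, which matches. The one-sided calculation gives 21 and does not match. At 50 per cohort, power is 0.977 for d = 0.80 and 0.697 for d = 0.50, and the difference detectable with 80% power is 0.566 SD.

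**2. Bias and false positives without adjustment.** Assumed, because the documents give no values: a covariate correlated r = 0.5 with the outcome within cohort, and a systematic shift s of 0.3 to 0.5 SD between cohorts.

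- Bias = r × s: 0.5 × 0.3 = 0.15 SD; 0.5 × 0.5 = 0.25 SD.
- Standard error of the difference at 50 per cohort = sqrt(2/50) = 0.20 SD.
- Noncentrality = 0.15/0.20 = 0.75 and 0.25/0.20 = 1.25.
- Two-sided rejection with no true effect, 98 df: 11.5% and 23.6%.

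**3. Precision after adjustment.** The ratio of adjusted to unadjusted standard error is sqrt((1 − R2y)/(1 − R2z)). R2y is the within-cohort outcome variance the covariates explain. R2z is the variance of the cohort indicator they explain. For one covariate shifted by s with equal groups, R2z = (s²/4)/(1 + s²/4): 0.022 at s = 0.3, 0.059 at s = 0.5, 0.20 at s = 1.

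| R2y (assumed) | s = 0.3 | s = 0.5 | s = 1 |
|---|---|---|---|
| 0.2 | 0.904 | 0.922 | 1.000 |
| 0.4 | 0.783 | 0.798 | 0.866 |

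At modest imbalance the standard error falls by about 8 to 22%. At R2y = 0.2 the gain has gone when the shift reaches 1 SD. Over R2y and R2z each from 0 to 0.3, the ratio runs from 0.84 to 1.20 and exceeds 1 whenever R2z > R2y. With 50 per cohort and four covariate parameters, power at d = 0.50 then runs from 0.54 to 0.84, against 0.697 unadjusted.

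The best case sets R2z = 0. The detectable difference is then 0.566 × sqrt(0.8) = 0.506 SD at R2y = 0.2 and 0.566 × sqrt(0.6) = 0.438 SD at R2y = 0.4, with power at d = 0.50 of 0.79 and 0.89. These figures assume balanced covariates, so they should not be combined with the bias figures in step 2.

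**4. Simulation** (50 per cohort, no true effect, 5,000 repetitions, assumed values; bias and SE in outcome SD).

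| Scenario | Unadjusted: bias, SE, false positives | Adjusted: bias, SE, false positives |
|---|---|---|
| No shift, slope 0.4 | 0.00, 0.199, 4.4% | 0.00, 0.183, 4.6% |
| Shift 0.5 SD, slope 0.4 | 0.20, 0.199, 16.5% | 0.00, 0.190, 4.9% |
| Shift 1 SD, slope 0.2 | 0.20, 0.200, 16.5% | 0.00, 0.220, 5.1% |
| Shift 0.5 SD, slope 0.4, plus 0.3 SD period effect | 0.50, 0.200, 69% | 0.30, 0.190, 35% |

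Adjustment removes the measured part of the bias in each case. In the third row it does so at the price of a larger standard error. In the last row the period effect stays in full.

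**5. Degrees of freedom.** Using 4 to 10 covariate parameters costs under 0.5 of a percentage point of power.

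**The case against.** **The t-test is not declared as the final analysis.** Section 7 uses it to size the study, and Section 9.7 does name regression. A reader might infer that the plan commits to an unadjusted t-test and nothing else. The documents do not support that: no analysis model, adjusted or unadjusted, is prespecified. It remains true that the t-test is the only between-cohort test named.

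**Not every covariate is certain to be recorded.** A reader might infer that age, ASA class and sedative or opioid use are all on file. Age and medications are listed in Section 4.5. ASA class appears only as an eligibility range, and a tick against I to III would satisfy Section 9.5.2. Sedative or opioid use would have to be coded from a general medication entry. This stands.

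**Adjustment is not free precision.** A reader might carry over from randomised trials the idea that it sharpens the estimate at no cost. With consecutive cohorts, covariates that differ by cohort inflate the standard error. This stands as a general caution, although at shifts of 0.3 to 0.5 SD in one covariate the inflation is small.

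**The bias figures rest on a systematic shift.** The chance standard error of a standardised covariate difference is sqrt(2/50) = 0.2 SD, so 0.5 SD is 2.5 standard errors, and chance imbalance is already within the t-test's 5%. No passage shows that case mix moves between periods. Excluding neurological disease and known drug abuse also narrows the variation. This limits the claim to what could happen. It does not remove the reason to adjust, since the design does nothing to prevent a shift.

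**The larger problem is untouched.** Cohort coincides with calendar period, and covariates cannot separate the two. That stands, but it is no reason to leave measured differences in the estimate.

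**Conclusion.** The point holds as a recommendation. The cohorts are unrandomised and consecutive, usable pre-anesthesia covariates are collected, and no adjusted comparison is specified. Under the assumed 0.3 to 0.5 SD shift and correlation of 0.5, an unadjusted comparison carries 0.15 to 0.25 SD of bias and a 12 to 24% false-positive rate at nominal 5%. Adjustment removes that part if the model form is right.

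Less bias is the main justification. A standard error lower by about 8 to 22% is probable if R2y is 0.2 to 0.4 and imbalance is modest, but it is not assured. Every driving input is an assumption. The documents do not show that an imbalance will occur, nor that an adjusted Cohort 3 versus Cohort 2 difference could be attributed to the algorithm alone.

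**What to change.** In Section 9.7:

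- Make the main comparison of each clinical measure a regression on cohort with a short fixed list of pre-anesthesia covariates: age (continuous), pre-operative sedative or opioid use coded from the recorded medications by a rule set in advance, and ASA class.
- Match the model to the outcome: log scale for wake-up time, a count model for somatic events, and an ordinal model for OAA/S where cohorts are compared on it.
- Report the unadjusted result beside the adjusted one.
- Confirm that the CRF records the ASA class itself, and add the field if it does not.
- State that adjustment does not remove calendar-time or unmeasured confounding from sequential enrolment. Concurrent or randomised allocation would be needed to address the former.

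Cost: protocol wording, coding of the medication entries, a few degrees of freedom and possibly one CRF field. No extra subjects or visits are needed.

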#### **4.6 Withdrawal of Subjects**

Informed consent discussions will explicitly include emphasis that neither patient enrollment nor patient withdrawal from the study will result in any alterations to the standard clinical care. Subjects may elect to withdraw at any time up to the induction of general anesthesia.

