## 6 STUDY PROCEDURES

### 6.1 Cohort Enrollment

Each cohort will enroll up to 50 subjects each. Subjects will be assigned to Cohort 1 until up to 50 subjects have been enrolled, after which subjects will be enrolled to Cohort 2. Cohort 2 will enroll up to 50 subjects, after which subjects will be enrolled to Cohort 3, which will enroll up to 50 subjects. All Cohorts will have equal sample sizes.

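### Does Section 7 overstate its power, given that enrolment has only a ceiling and d = 0.80 is tied to no outcome?

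*Combined protocol and SAP*

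**What the plan says.** Section 7 frames the comparison as a two-sample t-test between cohorts. It takes power 0.80 and alpha 0.05 as conventional, and describes Cohen's d as the expected difference in means "divided by the expected standard deviation, is usually set at 0.80". With equal groups and normal distributions it arrives at 26 per cohort. It then sets the enrolment ceiling of 50 against that number, "which would provide more than enough samples per Cohort to detect a difference between the outcome variables of the different Cohorts".

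The enrolment rules lie elsewhere:

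- Section 4.1: "Up to 50 subjects may be enrolled per Cohort".
- Section 6.1: "Subjects will be assigned to Cohort 1 until up to 50 subjects have been enrolled, after which subjects will be enrolled to Cohort 2". Cohort 3 follows Cohort 2 in the same way, and "All Cohorts will have equal sample sizes".
- Section 4.5, on signature of the consent form: "Now the patient will be enrolled as a study subject". Eligibility is described after that: "If a subject is deemed ineligible after screening, the subject will be withdrawn from the study".
- Section 4.6: "Subjects may elect to withdraw at any time up to the induction of general anesthesia".

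Aim Four in Section 2.1 names somatic events, anaesthetic drug use, wake-up times and PSI against OAA/S as comparison measures. Section 9.7 leaves the comparisons between cohorts optional.

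**The concern.** Section 7's conclusion carries no condition, yet it needs two.

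The first is size. Every enrolment statement gives an upper limit, and the 26 is never made a minimum. The 50 is counted at consent, before eligibility is confirmed, and no replacement rule or loss allowance is given. Because cohorts are filled in order, an early end to enrolment would fall on Cohort 3, the one that uses the investigational PSI. The equal-size rule fixes a ratio and not a number, so three cohorts of 20 would comply with it.

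The second is effect size. No outcome is given an expected difference or SD, so nothing shows that 0.80 SD is realistic. Section 1.1 describes the two PSI algorithms as similar, which gives no reason to expect a large gap between Cohorts 2 and 3.

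If either condition failed, the comparison behind Aim Four would be less sensitive than Section 7 implies, and a null result could be mistaken for evidence of comparable performance.

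**Working it through.** **Inputs.** From Section 7: two-sample t-test, alpha 0.05, power 0.80, d = 0.80, equal groups, normal outcomes. From Sections 4.1 and 6.1: at most 50 per cohort. Sidedness is not stated. Two-sided is inferred because it reproduces the plan's figure, whereas one-sided gives 21.

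**Reproducing the 26.** The normal approximation is n = 2(1.960 + 0.842)² / 0.80² = 15.70 / 0.64 = 24.5, or 25 per group. The exact noncentral-t solution is 25.52, which rounds up to 26. The plan's figure is correct.

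**Power at the plan's d.** The noncentrality is d × √(n₁n₂/(n₁+n₂)), with n₁ + n₂ − 2 degrees of freedom.

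| Analysed per cohort | Noncentrality | Power |
|---|---|---|
| 50 | 0.80 × √25 = 4.00 | 97.7% |
| 40 | 0.80 × √20 = 3.58 | 94.2% |
| 26 | 0.80 × √13 = 2.88 | 80.7% |
| 20 | 0.80 × √10 = 2.53 | 69.3% |
| 15 | 0.80 × √7.5 = 2.19 | 56.2% |

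The loss that still leaves 26 of 50 is (50 − 26)/50 = 48%.

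**Cohort 3 short, Cohort 2 full.** With 50 against 17, the noncentrality is 0.80 × √(850/67) = 2.85 and power is 80.2%. With 50 against 16, it is 0.80 × √(800/66) = 2.79 and power is 78.3%.

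**Multiplicity (an assumption; the plan states no adjustment).** Bonferroni over the three pairwise comparisons in Section 9.7 raises the requirement at d = 0.80 to 35 per cohort. Fifty per cohort then gives 93.9%.

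**Smaller effects, 50 per cohort.** Power is 80% at 0.57 SD, 69.7% at 0.5 SD and 31.8% at 0.3 SD. The 95% confidence interval for a difference in means has half-width 1.984 × √(2/50) = 0.40 SD. If 10% or 20% of the 50 were not analysed (assumed range), 80% power would start at 0.60 or 0.63 SD.

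**How likely is heavy loss?** The HIPAA text under Section 4.5 describes pre-screening of health information before consent. Section 9.1 draws candidates from the elective surgical schedule and has the attending surgeon confirm that each is appropriate. Section 4.4 limits participation to one visit that ends at wake-up in the operating room, so there is no follow-up period to lose subjects from. Late ineligibility, withdrawal before induction and unusable recordings remain possible, but nothing points to losses near 48%.

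**The case for a change.** The strongest case for a change is that a sample-size section should let the reader see what the study can and cannot detect, and this one does not. It supplies a d without an outcome and a maximum without a minimum. A modest difference between two versions of one index is plausible, and at 0.3 to 0.5 SD even full cohorts give only 32% to 70% power. Stating a target, a minimum and these figures would be cheap.

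The factual part of this stands: no minimum is stated, Cohort 3 is filled last, and 0.80 is a convention. The inference is weaker. Cohorts of 15 or 20 are hypothetical, and a full Cohort 2 beside a depleted Cohort 3 would depart from Section 6.1, not follow from it. The word similar in Section 1.1 describes the algorithms and says nothing about the size of any effect on outcomes.

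The obvious remedies also gain little. A binding minimum of 26 would come only from the d = 0.80 that is said to lack support. Requiring Cohort 3 to match Cohort 2's analysed number under a ceiling of 50 enrolled could leave enrolment unable either to close or to continue, for example with 48 analysed in Cohort 2 and 46 of 50 in Cohort 3. A power statement in SD units would not carry over directly to event frequency or to PSI against OAA/S, both listed in Aim Four.

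**Conclusion.** No change is needed. Section 7's arithmetic is right, and its conclusion holds at its stated d for any equal cohorts of 26 or more analysed, with 98% power at the ceiling. The gap is one of detail: an effect size chosen by convention and an enrolment target written as a maximum. Section 9.7 sets no success criterion that depends on the power claim, so restating the sensitivity would not alter an analysis or correct a wrong result.

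Analysts can fill the gap when reporting. They can give the numbers analysed in each cohort, report differences between cohorts with confidence intervals, and not read a non-significant Cohort 3 against Cohort 2 result as proof of comparable performance, since the interval would extend about 0.40 SD either side of the estimate at 50 per cohort.

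This conclusion assumes a two-sided test, approximately normal continuous outcomes, and cohorts kept equal as Section 6.1 requires. It does not show that 0.80 SD is a realistic difference for any outcome, and the plan offers no figures with which to judge that. It covers the text supplied, from which some pages had been removed.

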### **8 SAFETY AND ADVERSE EVENTS**

#### **8.1 Definitions**

The definitions for adverse event, adverse device effect, serious adverse event, serious adverse device effect, and unanticipated adverse device effect are provided below (ISO 14155:2011, 21 CFR 812.3(s)).

- Adverse Event (AE): an adverse event is any untoward medical occurrence in a subject which need not be related to the device under investigation.
- Adverse Device Effect (ADE): an adverse device effect is any untoward or unintended response to a medical device which may result from insufficiencies in the instructions for use or deployment of the device, or from use error.
- Serious Adverse Event (SAE): a serious adverse event is an adverse event that results in death, inpatient hospitalization, severe or permanent disability, a life threatening illness or injury, fetal distress, fetal death, a

congenital abnormality, a birth defect, or medical or surgical intervention to prevent permanent impairment to body or structure.

- Serious Adverse Device Effect (SADE): a serious adverse device effect is an adverse device effect that results in death, inpatient hospitalization, severe or permanent disability or is life threatening.
- Unanticipated Adverse Device Effect (UADE): any serious adverse effect on health or safety or any life threatening problem or death cause by or associated with, a device, if the effect, problem, or death was not previously identified in nature, severity or degree of incidence in the investigational plan, or application (including a supplementary plan or application) or any other unanticipated serious problem associated with a device that related to the rights, safety or welfare of subjects. Refer to the Device Risk Analysis and Risk Assessment section for details on anticipated adverse device effects.

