## **8.3 Adverse Event Reporting:**

- All Adverse Events, both Anticipated and Unanticipated, must be recorded in the CRF and recorded in detail in the Adverse Event Report Form.
- All Adverse Events must be promptly reported to the Sponsor.
- All Unanticipated Adverse Device Effects will be also reported to both the Sponsor and the IRB.
- Both Serious Adverse Events and Unanticipated Adverse Device Effects must be reported to the Sponsor within 48 hours. All other Adverse Events should be reported to the Sponsor within 5 business days.
- All Serious Adverse Events will be also reported to the IRB per IRB reporting requirements. These reports may include, but will not be limited to: date of onset; brief description of the events; their treatment; whether they resulted in death, inpatient hospitalization, severe or permanent disability or were life threatening; their relationship to the study device; and resolution.

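### The SAE definition omits prolongation of an existing hospital stay, so an event serious only on that ground takes the slower reporting route; separately, the SADE criteria do not match the SAE criteria

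*Combined protocol and SAP*

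**What the plan says.** **SAE (8.1).** The protocol says "a serious adverse event is an adverse event that results in death, inpatient hospitalization, severe or permanent disability, a life threatening illness or injury". The list goes on to fetal and birth outcomes and to "medical or surgical intervention to prevent permanent impairment to body or structure". A prolonged stay is not among the criteria, and the idea appears nowhere else in the document.

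**SADE (8.1).** The protocol says "a serious adverse device effect is an adverse device effect that results in death, inpatient hospitalization, severe or permanent disability or is life threatening". There is no intervention criterion and no prolongation criterion.

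**AE (8.1).** The scope is wide: "an adverse event is any untoward medical occurrence in a subject which need not be related to the device under investigation".

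**Reporting (8.3).** The fast clock is "Both Serious Adverse Events and Unanticipated Adverse Device Effects must be reported to the Sponsor within 48 hours". For the rest, "All other Adverse Events should be reported to the Sponsor within 5 business days". SAEs and UADEs also go to the IRB. No IRB route is stated for an event that is neither. SADE does not appear as a trigger.

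**Population and visit.** Section 4.2 requires "Subjects undergoing general surgery" and does not say whether they are inpatients or day cases. Under Section 4.4 the visit, and with it data collection, closes when the subject wakes in the operating room.

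**The concern.** For a subject already admitted, an event cannot newly cause an admission, so the hospitalization criterion has nothing to act on. If the event's only serious consequence is a longer stay, no other criterion picks it up. The same event in a day-case subject who then has to be admitted is an SAE. On this one criterion, classification depends on where the subject started and not on what the event did.

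What is at stake is the reporting route. The event would reach the sponsor on the slower clock and might not reach the IRB. Section 11 plans no safety board, so the classification carries some weight. In Cohort 3 the provider may use an investigational index in managing anesthesia, and wake-up time and drug use are comparison measures (Sections 2.1 and 6.5). A longer stay after slow emergence is therefore a conceivable consequence that need not be life threatening or disabling.

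The mismatch between the SADE and SAE lists is a separate matter. It raises the question of whether some serious device effects are labelled inconsistently.

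**Working it through.** The plan states no figure on this point, so there is nothing to reproduce. The check sets the definitions in 8.1 against the triggers in 8.3.

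**Step 1. Which events are affected by the missing prolongation criterion?**

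| Consequence of the event | Admitted subject | Day-case subject |
|---|---|---|
| Death, life-threatening illness or injury, severe or permanent disability | SAE | SAE |
| Intervention needed to prevent permanent impairment | SAE | SAE |
| Extra time in hospital only | Not an SAE as written | SAE if the event leads to admission |

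Only the last row depends on admission status.

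**Step 2. What does that row cost in time?** Inputs are 48 hours and 5 business days, both from 8.3. The section does not say when either clock starts; I assume the same start for both. Converting business days to hours is also my assumption, ignoring holidays:

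- No full weekend crossed: 5 × 24 = 120 h, and 120 − 48 = 72 h later.
- One weekend crossed: 7 × 24 = 168 h, and 168 − 48 = 120 h later.

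The latest permitted sponsor notice is thus 72 to 120 h later. On the IRB side, the event moves from a stated route to none, unless it is a UADE.

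**Step 3. Does the SADE omission delay anything?** Take a device effect whose only serious feature is that it needed intervention to prevent permanent impairment. It is an untoward occurrence, so it is an AE. It meets the intervention criterion, so it is an SAE. Under 8.3 it is due in 48 hours and goes to the IRB. Its SADE label plays no part, so the difference in deadline is 0 h. The label matters only where SADEs are counted. Section 10.5 has the monitor verify documentation of SAEs and SADEs, and there this effect would appear as an SAE but not as an SADE.

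**Step 4. How many subjects could be exposed?** The inpatient share is not given. As assumptions, 30%, 60% and 90% of the maximum 150 subjects are 150 × 0.30 = 45, 150 × 0.60 = 90 and 150 × 0.90 = 135. These are subjects for whom the hospitalization criterion could not operate. They are not events.

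**The case against.** The strongest reply is that the affected class may be very small, or empty. Every grave consequence other than a longer stay remains an SAE whatever the admission status. A reader might infer that complications in admitted surgical patients are in general graded non-serious and reported late. The table above shows that the text does not support this.

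Other parts of the reply:

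- **UADE route.** That definition uses the word serious without tying it to the SAE list, and it has a catch-all for unanticipated serious problems associated with a device. Section 8.2 anticipates only mild allergic and skin reactions. A device-associated event could therefore still reach the sponsor in 48 hours and the IRB. This stands for device-associated events judged serious in that general sense; it does not help with events unrelated to the device.
- **SADE and lateness.** A reader might infer that the narrower SADE list also delays reports. It does not, because 8.3 is triggered by SAE and UADE.
- **IRB report content.** The last bullet of 8.3 repeats a list of outcomes close to the SADE list, and a reader might take this as narrowing what the IRB receives. The bullet says that its items are not exhaustive, and it includes the treatment given, so it narrows nothing.
- **End of visit.** Section 4.4 closes data collection at wake-up and no later AE window is stated, so a longer stay would usually not be known by then. This limits the practical gain from changing the definition. It does not remove the gain, because an event that began during the visit can still be classified on its consequences afterwards.
- **Other safeguards.** All AEs are to be recorded and promptly reported, monitors check the documentation, and the investigator evaluates every AE (Sections 8.3, 10.5 and 14). The reporting route is one check among several.

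**Conclusion.** The point holds in narrow form and is minor. As written, an event in an already-admitted subject that is serious only because it lengthens the stay is non-serious. It is due to the sponsor 72 to 120 h later than an SAE, on the conversion assumed above, and has no stated IRB route unless it is a UADE. The SADE and SAE criteria are inconsistent. That changes no deadline but can under-count serious device effects in the monitor's SAE/SADE check.

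The conclusion rests on a literal reading of 8.1 and on some subjects being inpatients, which the plan neither states nor excludes. A reader might treat 45, 90 or 135 exposed subjects as the size of the problem. The documents do not support that: the shares are assumed, no event rate is given, and the number of affected events could be zero. No sample size, power or analysis figure is touched.

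**What to change.** 1. In 8.1, change the SAE criterion to: *inpatient hospitalization or prolongation of existing hospitalization*.
2. In 8.1, define SADE as an adverse device effect that meets any SAE criterion, so that the two lists cannot diverge.
3. Because data collection ends at wake-up (4.4), state that the seriousness of an event with onset during the visit is judged on its later consequences. Without this, the first change would have little effect.

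No change is needed to the 8.3 content list. The documents give no basis for going further, for example by naming unplanned transfer to a higher level of care as a criterion of its own.

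The cost is a short amendment under Section 13.2 and an edit to the Adverse Event Report Form. The third change also means that someone at the site must learn the later outcome of events that began in the operating room. The downside is a few more 48-hour reports, some of them for expected surgical complications.
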